11.5.3 Pooling

Subgroup analysis of the primary efficacy endpoint by comparing clinical centers will be used to evaluate the poolability of the results. Treatment by center interaction will be tested in the primary analysis model at a significance level of 10%. This interaction term is not part of the primary endpoint model. If the interaction is found significant the reason for this interaction will be further explored and rationalized. This evaluation may include demographic features, symptoms at presentation, and clinical and treatment history, and center comparability in the features found to be associated with the primary efficacy variable.

In the case that poolability is questionable, the reasons for differential treatment effect, such as subject and clinical characteristics, will be investigated and reported.

11.5.4 Secondary Efficacy Endpoint Analyses:

- Proportion of responder subjects- defined as the percent of subjects achieving at least 50% reduction from baseline in their HDRS-17 total score, 8 weeks post Relivion®DP treatment initiation - will be summarized by a count and percentage and compared between the groups with a chi-squared test and a Fisher's exact test. The odds ratio with 95% Wald confidence interval will be presented as well. As an additional measure of effect size the NNT will be presented. If covariates are identified in the prognostic factor analysis, logistic regression will be performed as well adjusting for the identified factors.
- Proportion of subjects achieving remission- defined as the percent of subjects with HDRS-17 score≤7 at 8 weeks post Relivion®DP treatment initiation- will be summarized by a count and percentage and compared between the groups with a chi-squared test and a Fisher's exact test. The odds ratio with 95% Wald confidence interval will be presented as well. As an additional measure of effect size the NNT will be presented. If covariates are identified in the prognostic factor analysis logistic regression will be performed as well adjusting for the identified factors.

- Mean change in depressive symptoms, measured by MADRS total score, from baseline to week-8 post treatment initiation - will be compared between the groups using a similar model as the primary endpoint.

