8.2 Secondary Efficacy Endpoints

Secondary efficacy endpoints include:

- **Proportion of responder subjects** - defined as the percent of subjects achieving at least 50% reduction from baseline in their HDRS-17 total score, 8 weeks post Relivion®DP treatment initiation.

- **Proportion of subjects achieving remission** - defined as the percent of subjects with HDRS-17 score≤7 at 8 weeks post Relivion®DP treatment initiation.
- **Change from baseline** to week-8 post Relivion®DP treatment initiation **in depressive symptoms** as measured by **MADRS** total score.

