- Each HDRS 17/21 item separately at baseline.
- Total HDRS 17/21 scores at baseline.
- Each separate MADRS item at baseline.
- Total MADRS scores at baseline.
- Baseline CGI-S scores.
- Baseline C-SSRS score Lifetime/ past 12 months.
- Baseline QIDS-16 score.

To assess correlation of the listed variables with the primary efficacy endpoint change from baseline HDRS-17 score to week 8 an ANOVA model will be used, entering each variable univariately as the independent variable. The same will be done for change from baseline HDRS-17 score to week 4.

To assess correlation of the listed variables for the binary variables (response and remission) a logistic regression model will be used, entering each variable univariately as the independent variable. The same will be done for change from baseline HDRS-17 score to week 4.

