11.5 Endpoints Analyses

11.5.1 Primary Efficacy Endpoint Analyses

The primary efficacy endpoint is the change from baseline to 8 weeks post treatment initiation in HDRS-17 score.

The change in HDRS-17 from baseline to 8 weeks post treatment initiation will be compared between the treatment groups using a repeated measures analysis of covariance (ANCOVA, SAS® MIXED procedure). The model will include the following fixed effects: treatment group, visit, treatment group by visit interaction

with Baseline HDRS-17, and center entered as covariates. If covariates are identified in the prognostic factor analysis, they may be added to the model as well. Baseline HDRS-17 scores will be entered as a continuous variable so that the potential for co-linearity problems will be minimized. The treatment group by center interaction will be evaluated as well, but not as part of the principal statistical evaluation.

The unstructured covariance matrix structure will be used. If the model does not converge, then either the compound symmetry or autoregressive (whichever model has the lower AIC statistic) covariance matrix structure will be used instead. At this time point (up to 8 weeks) we do not expect a high proportion of dropouts, as a placebo effect of the sham treatment is expected and was taken into consideration in the design of the study. Thus, any missing data at 8 weeks post treatment initiation can be considered missing at random. Therefore, since repeated measures ANOVA is also an imputation method, for this evaluation no other method of imputation of missing data is considered beyond the model estimates. Nevertheless, should the missing at random assumption prove to be incorrect, a sensitivity analysis using other methods for data imputation mentioned in Section 7 may be performed.

Mock SAS code for the analysis:

```
Proc Mixed data=HDRS17;
  class visit group center subjectid;
  model change_HDRS17 = baseline_HDRS17 visit group visit*group;
  repeated / type=un subject=subjectid;
  lsmeans group*visit / pdiff cl;
  random center;
run;
```

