- **Proportion of subjects achieving remission at visit 6** - defined as the percent of subjects with HDRS17 score≤7 at 16 weeks post Relivion®DP treatment initiation in the original active group. The percent of subjects achieving remission at each visit in the original active group will be summarized by a count and percentage and compared between the visits using a GEE model (repeated measures model for binary data) programmed in the SAS GENMOD Procedure which will account for the within subject correlation, baseline HDRS-17 score will be entered as a covariate.
- **HDRS-17 Category Shift from Visit 2 to Visit 6** – defined as the category change from baseline to week-16 post Relivion®DP treatment initiation in HDRS-17; Categories definition: 5: Very severe 26-52, 4: Severe 20-25, 3:

Moderate 14-19, 2: Mild 13-8 and 1: 0-7 Remission. The category shift will be tabulated and summarized by a count and percent.

- **Proportion of new responder subjects** - defined as the percent of subjects who did not have a remission (per HDRS-17) at visit 4, achieving at least 50% reduction from baseline (Visit 2) in HDRS-17 total score 16 weeks post Relivion®DP active treatment initiation (Visit 6). A count and percentage with two-sided exact 95% confidence interval will be presented.
- **Proportion of new subjects achieving remission** - defined as the percent of subjects who did not have a remission (per HDRS-17) at visit 4, achieving a HDRS-17 total score \leq 7 points 16 weeks post Relivion®DP active treatment initiation (Visit 6). A count and percentage with two-sided exact 95% confidence interval will be presented.
- **Change from baseline to 16 weeks (Visit 6) post Relivion®DP treatment initiation in the Clinical Global Impression Severity scale (CGI-S) score.** The change from baseline CGI-S score will be modeled with a repeated measures ANCOVA model. The change will be modeled as a function of visit (categorical) with baseline value entered as a covariate. LSmean CGI-S changes from baseline will be estimated from the model per visit and for the difference between visits and will be presented with 95% confidence intervals as well as level of significance (testing the null hypothesis LSmean=0). The change at visit 6 will also be compared to the change at visit 4.

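### The stated tests of week-8 remission ignore baseline HDRS-17; fixing it in advance as a covariate would add roughly 1 to 6 points of power at almost no cost

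*SAP*

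**What the plan says.** SAP 8.2 makes remission a secondary endpoint, "defined as the percent of subjects with HDRS-17 score≤7 at 8 weeks post Relivion®DP treatment initiation". SAP 11.5.4 summarizes it by counts and percentages, to be "compared between the groups with a chi-squared test and a Fisher's exact test", with a Wald interval for the odds ratio and an NNT. Adjustment enters only conditionally: if the prognostic factor analysis identifies covariates, "logistic regression will be performed as well adjusting for the identified factors". Baseline severity is one entry on the long candidate list in SAP 11.4 ("Total HDRS 17/21 scores at baseline"). That section announces a threshold for inclusion, but its text states none.

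The continuous endpoints are treated differently. The primary model in SAP 11.5.1 has its fixed effects "with Baseline HDRS-17, and center entered as covariates", and "Baseline HDRS-17 scores will be entered as a continuous variable". The MADRS change uses a similar model. SAP 11.4 itself argues that ANCOVA adjustment reduces bias and improves precision and power, and it names response and remission among the results open to challenge if unadjusted.

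Under SAP 9.2, remission is one of three secondary endpoints tested after the primary with a Benjamini-Hochberg adjustment. The tertiary endpoints follow only if the primary and secondary endpoints are significant.

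**The concern.** A fixed threshold on the week-8 score is strongly tied to where a subject starts. Suppose baseline mean 22, SD 4 and a baseline/week-8 correlation of 0.5 (all assumed), with the plan's change SD of 6 and a mean change of -8.4. Predicted active-arm remission is then about 33% for a subject starting at 18 and about 5 to 6% for one starting at 26 (arithmetic below). The strata in SAP 11.5.2 (17-19, 20-25, 26 or more) show that such a spread is expected.

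The crude tests leave this known source of variation in the comparison although the value is scheduled to be collected from every subject before randomization. Two things are at stake: some power on an endpoint that has little to spare, and a crude remission difference and NNT that carry any chance baseline imbalance.

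**Working it through.** **The plan's own figure.** Protocol 12.4 assumes a 3.3-point difference, SD 6, two-sided 5% and 80% power.
- Normal approximation: n = 2(1.96 + 0.84)² × 6² / 3.3² ≈ 52 per group.
- Two-sample t-test: 52.9, so 53 per group (power 80.1%). This reproduces the plan.
- Dropout: 106/0.85 = 124.7, against 124 stated, which is immaterial.
- No power for remission is stated.

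**Model on the HDRS scale.** The active mean change is -8.4 (6-week feasibility result, protocol 12.4) and the sham change is -8.4 + 3.3 = -5.1, with 53 per arm. Assumed: baseline mean 19 or 22, baseline SD σb of 3 or 4, and correlation ρ. The week-8 SD σw is set so that the change SD is 6:

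σw = ρσb + √(36 − (1 − ρ²)σb²)

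For σb = 4 and ρ = 0.5, σw = 2 + √24 = 6.90. The slope on baseline is 0.5 × 6.90/4 = 0.86 and the residual SD is 6.90 × √0.75 = 5.97. With mean 22 and change -8.4:
- start at 18: expected week-8 score 13.6 − 3.4 = 10.2; P(7 or less) = Φ((7.5 − 10.2)/5.97) ≈ 33%
- start at 26: expected 13.6 + 3.4 = 17.0; Φ((7.5 − 17.0)/5.97) ≈ 5 to 6%

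**Plausible correlation.** If change were unrelated to baseline, ρ = σb/√(σb² + 36), which is 0.45 at SD 3 and 0.55 at SD 4. Entry restrictions narrow the baseline range and lower it.

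**Remission power, crude chi-squared against the adjusted logistic score test** (two-sided 5%; 2,000 trials per untruncated scenario, Monte Carlo SE about 1.1 points per figure; 3,000 per truncated scenario):

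| Scenario | Chi-squared | Adjusted | Gain (points) |
|---|---|---|---|
| ρ 0.5, mean 19, untruncated | 0.42-0.45 | 0.48-0.50 | 4-6 |
| ρ 0.5, mean 22, untruncated | 0.32-0.34 | 0.36-0.39 | 4-6 |
| ρ 0.5 before truncation at 17, mean 19 | 0.411; 0.435 | 0.434; 0.463 | 2.3; 2.8 |
| ρ 0.5 before truncation at 17, mean 22 | 0.315; 0.331 | 0.345; 0.352 | 3.0; 2.1 |
| ρ 0.3, either baseline | | | about 1-2 |

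Truncation at 17, the lowest stratum in SAP 11.5.2, lowers the realised correlation from 0.5 to 0.37-0.45.

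**Second model, anchored on a remission rate.** The only rate in the documents is 35% (8/23, 6-week open-label study, protocol 7.6.2). Shifting it by d = 3.3/6 = 0.55 on a normal scale gives sham 17.5%. Results at ρ = 0.5 (6,000 trials per scenario):

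| Active vs sham | Chi-squared | Likelihood ratio | Wald |
|---|---|---|---|
| 25% vs 11% | 46.5% | 52.7% | 49.0% |
| 35% vs 17.5% | 55.2% | 61.9% | 59.6% |
| 45% vs 25% | 60.0% | 66.6% | 65.1% |

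The likelihood-ratio gain is 6.2 to 6.7 points and the Wald gain 2.5 to 5.1. At ρ = 0.3 the likelihood-ratio gain is 1.3 to 3.0 and Wald runs from about -1 to 0. With baseline truncated at 17 but a realised correlation of 0.53, the gain is 4.6 (Wald) to 6.5 (likelihood ratio). The realised correlation is therefore what matters, not truncation as such.

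**Choice of statistic.** In the truncated runs with mean 22, the adjusted Wald test had less power than chi-squared (0.273 against 0.315; 0.299 against 0.331), because sham remissions are few.

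**Type I error** at equal 35% rates, ρ = 0.5: chi-squared 5.4%, Fisher 3.4%, likelihood ratio 5.2%, Wald 4.8%.

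**Chance imbalance.** The SE of the baseline mean difference is σb√(2/53) = 0.194σb, or 0.58 points at SD 3 and 0.78 at SD 4. At ρ = 0.5, a one-SE imbalance moves the remission difference by about ρ × 0.194 × the mean normal density at the two cut-points = 0.5 × 0.194 × 0.31 = 3.0 percentage points, against an expected 35 − 17.5 = 17.5.

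**The case against.** The best defence is that the plan already provides for adjustment. Baseline HDRS total is a named candidate, and the screen fits it by logistic regression against remission. If one assumes a 5% screen, baseline would be selected in about 91 to 97% of trials at correlation 0.5, or 71 to 84% with truncation. An adjusted result would then usually appear beside the crude one. That stands, so it would be wrong to infer that the plan never adjusts remission for baseline. But the adjusted analysis is conditional and additional, and nothing makes it the test that counts.

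The gain also rests on a correlation that the documents do not give, and at 0.3 it is small. That stands too, and it is why a range is given.

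Stronger readings are tempting but not supported:
- That the crude test is invalid. Its type I error is close to nominal.
- That 9 to 13 points are lost. This needs a correlation of 0.7, for which the documents offer no basis.
- That 12 to 17 points are lost against Fisher's test. Some 8 to 10 of those are Fisher's own conservatism.
- That two-point baseline imbalances are a realistic worry. They occur in about 1% of trials or fewer.
- That the open-label remission model, where "baseline HDRS-17 score will be entered as a covariate", is a direct precedent. It compares visits within the original active group, not arms.
- That access to the tertiary endpoints is materially harmed. The power figures above are at an unadjusted 5%, and the effect through the Benjamini-Hochberg step has not been quantified.

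**Conclusion.** The point holds as a matter of efficiency, not validity. The stated between-arm tests of remission omit a baseline value that the plan treats as essential for the primary endpoint. Fixing it in advance would add roughly 1 to 6 points of power with a score or likelihood-ratio test: about 4 to 6 at correlation 0.5 with an untruncated baseline, about 2 to 3 (score test) with baseline truncated at 17, and about 1 to 2 (score test) at correlation 0.3. The likelihood-ratio test runs slightly higher than the score test. These figures rest on the plan's 3.3-point difference, change SD of 6 and 53 per arm, and on assumed baseline mean, SD and correlation.

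Remission power is only about 0.3 to 0.6 in these scenarios, so even a small gain at negligible cost is worth having. Adjustment would also take chance baseline imbalance (SE about 0.6 to 0.8 points at SD 3 to 4) out of the reported remission difference and NNT. The case is mainly for remission: response gains only about 0 to 2 points at correlation 0.5.

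**What to change.** In SAP 11.5.4, name as the deciding test for remission a logistic regression on treatment arm and continuous baseline HDRS-17, fixed regardless of the prognostic screen. Specify a likelihood-ratio or score test, not Wald, because Wald can lose power when remissions are few. From that model, report the standardized risk difference and NNT with 95% CI. Keep counts, percentages, chi-squared and Fisher as supportive. Using the same model for response is optional.

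This also settles which p-value enters the Benjamini-Hochberg step in SAP 9.2; SAP 11.5.4 lists both crude tests without saying which decides.

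The cost is a few sentences and lines of code, provided that the change is made before the treatment code is opened (SAP 6 states that it had not been revealed when the SAP was finalized). There are two small downsides. The model's odds ratio is conditional on baseline, so the standardized risk difference should be the headline. A penalized or exact fit should be named as fallback in case remissions are very few.

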11.5.5 Tertiary Endpoints Analyses

- Mean Change in the CGI-S score - at 8 weeks post treatment initiation– will be compared between the groups using a similar model as the primary endpoint.
- Mean CGI-I scores at 8 weeks post treatment initiation will be compared between the groups using a similar model as the primary endpoint but with the value at each visit modeled instead of the change.
- Mean change from baseline in total score of the Quick Inventory of Depressive Symptomatology self-rated (QIDS-SR-16) score at 8 weeks post treatment initiation– will be compared between the groups using a similar model as the primary endpoint.
- Mean change in depressive symptoms, measured by HDRS-21 total score, from baseline to week 8 post Relivion®DP treatment initiation will be compared between the groups using a similar model as the primary endpoint.
- Proportion of subjects with a clinically substantial reduction in HDRS-17 score defined as the percent of subjects with reduction in HDRS-17 score of at least 7 points at 8 weeks post Relivion®DP treatment initiation - will be summarized by a count and percentage and compared between the groups with a chi-squared test and a Fisher's exact test. The odds ratio with 95% Wald confidence interval will be presented as well. As an additional measure of effect size the NNT will be presented.
- HDRS-17 total score at visit 4 (week-8 post Relivion®DP treatment initiation) will be compared between the groups using a similar model as the primary endpoint using the HDRS-17 score at each visit instead of the change.
- HDRS-17 Category Shift from Visit 2 to Visit 4 – defined as the category change from baseline to week-8 post Relivion®DP treatment initiation in HDRS-17; Categories definition: 5: Very severe 26-52, 4: Severe 20-25, 3: Moderate 14-19, 2: Mild 13-8 and 1: 0-7 Remission, will be summarized by a count and

percentage and compared between the groups with a Cochran-Armitage trend test.

- Mean change in Q-LES-Q score at visit 4 – measured as the difference between the baseline and visit 4 Q-LES-Q percentage of maximum total scores, will be compared between the groups using analysis of variance (ANOVA).

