8.3 Tertiary Efficacy Endpoints

Tertiary Efficacy endpoints include:

- **Change from baseline** to 8 weeks post Relivion®DP treatment initiation **in the Clinical Global Impression Severity scale (CGI-S) score**.
- **Clinical Global Impression Improvement (CGI-I) score** over time **to Visit 4**.
- **Change from baseline** to week-8 post Relivion®DP treatment initiation **in the total score of the Quick Inventory of Depressive Symptomatology (self-rated)** (QIDS-SR-16).
- **Change from baseline** to week-8 post Relivion®DP treatment initiation **in depressive symptoms** as measured by **HDRS-21** total score.
- **HDRS-17 Total score** to week-8 post Relivion®DP treatment initiation.
- **Proportion of subjects achieving clinically substantial improvement in HDRS-17** - defined as the percent of subjects with reduction in HDRS-17 score of at least 7¹ points at 8 weeks post Relivion®DP treatment initiation.
- **HDRS-17 Category Shift from Visit 2 to Visit 4** – defined as the category change from baseline to week-8 post Relivion®DP treatment initiation in HDRS-17; Categories definition: 5: Very severe 26-52, 4: Severe 20-25, 3: Moderate 14-19, 2: Mild 13-8 and 1: 0-7 Remission.
- **Change from baseline Q-LES-Q score at Visit 4** – measured as the difference between the baseline and visit 4 Q-LES-Q percentage of maximum total scores.

¹ Rush AJ et al. Clinically Significant Changes in the 17- and 6-Item Hamilton Rating Scales for Depression: A STAR*D Report. Neuropsychiatric Disease and Treatment 2021;17:2333–2345

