9. SIGNIFICANCE LEVELS AND HANDLING OF TYPE I ERROR

9.1 Type I error

The overall significance level for this study is 5% using two-tailed tests, except for treatment by site interaction that will be tested at a significance level of 10% and the test for early efficacy at the interim look.

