9.2 Hierarchy Approach for The Primary and Secondary Endpoint Analysis

The hierarchy approach will be adopted for the primary and secondary endpoints to control type I error due to multiple endpoint testing. Thus, the primary endpoint will first be tested and only if $p \leq .05$, will the secondary endpoints be tested. For the three secondary performance endpoints, the Benjamini–Hochberg step-up method will be used to adjust the p-values. If the primary and the secondary endpoints are found statistically significant then the hierarchy will be extended to include the tertiary endpoints for the seven tertiary performance endpoints, the Benjamini–Hochberg step-up method will be used to adjust the p-values.

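### SAP 9.2 sizes the tertiary step-up for seven endpoints but eight are listed, and one of the eight (HDRS-17 total score) is in effect the primary test again

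*SAP*

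**What the plan says.** SAP 9.2 sets a three-step hierarchy. The primary comes first: "the primary endpoint will first be tested and only if" its p-value is at most 0.05 are the secondaries tested. Then: "If the primary and the secondary endpoints are found statistically significant then the hierarchy will be extended" to the tertiary endpoints, with a Benjamini–Hochberg step-up "for the seven tertiary performance endpoints". The level comes from SAP 9.1: "The overall significance level for this study is 5% using two-tailed tests".

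SAP 8.3, under "Tertiary Efficacy endpoints include", lists eight entries, and SAP 11.5.5 gives an analysis for the same eight:

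1. CGI-S change
2. CGI-I score
3. QIDS-SR-16 change
4. HDRS-21 change
5. "HDRS-17 Total score" at week 8
6. HDRS-17 reduction of at least 7 points
7. HDRS-17 category shift
8. Q-LES-Q change

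For entry 5, SAP 11.5.5 prescribes a comparison "using a similar model as the primary endpoint using the HDRS-17 score at each visit instead of the change". The primary model, in the mock code of SAP 11.5.1, is "model change_HDRS17 = baseline_HDRS17 visit group visit*group", with unstructured covariance and a random center term.

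**The concern.** Two things go wrong together. First, the family size is the divisor in every step-up threshold. With seven stated and eight listed, whoever programs the analysis has to guess either the divisor or the omitted endpoint.

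Second, entry 5 looks like the primary analysis under another name. A hypothesis that must be rejected before the family opens adds nothing as a member of that family. In a step-up procedure, though, a small p-value carried in from outside can help other endpoints over the line. What is at stake is how strictly the tertiary claims are tested.

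**Working it through.** **Count.** Stated: 7 (SAP 9.2). Listed: 8 in SAP 8.3 and the same 8 in SAP 11.5.5. The stated figure does not reproduce.

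**Is entry 5 the primary test?** Write Y for the score at a post-baseline visit and B for baseline, so change = Y − B. The primary model is

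Y − B = β·B + (visit, group, visit×group) + center + error.

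Adding B to both sides gives

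Y = (β + 1)·B + (the same terms) + center + the same error.

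Only the baseline slope moves, by 1. The residuals, and therefore the likelihood, the covariance estimates and the week-8 group contrast, are unchanged. Fitting both forms by REML to two simulated trials (106 subjects, random center, about 10% missing at week 8) confirms it:

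| Model | Dataset 1: contrast (SE), z | Dataset 2: contrast (SE), z |
|---|---|---|
| Change, baseline kept | −4.35193 (1.21685), −3.5764 | −3.38572 (1.13624), −2.9798 |
| Score, baseline kept | −4.35193 (1.21685), −3.5764 | −3.38572 (1.13624), −2.9798 |
| Score, baseline dropped | −4.33556 (1.21274), −3.575 | −3.28621 (1.20636), −2.724 |

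The identity therefore needs the baseline covariate to stay and the same post-baseline visits to be modelled.

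**Thresholds.** The k-th smallest of m p-values is compared with k × 0.05/m.

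- Clean family of seven: the first threshold is 0.05/7 = 0.00714.
- Eight with divisor 8: the first two are 0.05/8 = 0.00625 and 2 × 0.05/8 = 0.0125.
- Eight with divisor 7: the first two are 0.00714 and 2 × 0.05/7 = 0.0143.

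If the duplicate has p ≤ 0.0125 (divisor 8), any other endpoint with p ≤ 0.0125 makes at least two p-values at or below the second threshold, and both are rejected. The effective first threshold for the other seven is then 0.0125. If the duplicate's p is well above 0.0125 it rarely helps, and the first threshold is 0.00625, below the clean 0.00714.

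**Chance of any false claim when the other seven are all null.** Using the first threshold alone, with independence:

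- 0.00714: 1 − (1 − 0.00714)^7 = 4.9%
- 0.0125: 1 − (1 − 0.0125)^7 = 8.4%
- 0.0143: 1 − (1 − 0.0143)^7 = 9.6%

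Simulation of the full step-up (1,000,000 replicates) adds the later ranks:

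| Family | Primary p | Independent | Correlation 0.5 |
|---|---|---|---|
| Seven, no duplicate | any | 5.0% | 4.4% |
| Eight, divisor 8 | ≤ 0.0125 | 8.5% | 7.0% |
| Eight, divisor 8 | 0.013 to 0.049 | 4.6% to 4.4% | 4.4% to 3.9% |
| Eight, divisor 7 | ≤ 0.014 | 9.7% | about 8% |
| Eight, divisor 7 | 0.015 to 0.049 | 5.3% to 5.0% | 5.0% to 4.4% |

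**How often is the primary p at most 0.0125?** Inputs from protocol 12.4: difference 3.3, SD 6 (d = 0.55), 53 per group, two-sample t-test. Power at 0.05 is 80.1%, which reproduces the planned 80%. Power at 0.0125 is 61.5%. So 61.5/80.1 = 77% of significant primary results fall in the loosening range. Averaged over significant primaries (divisor 8, independent), the chance is about 0.77 × 8.5% + 0.23 × 4.4% = 7.6%, against 5.0%.

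**False discovery bound with divisor 7 on eight tests.** 8 × 0.05/7 = 5.7% instead of 5%. That bound counts all eight as null. If the HDRS-17 effect is real, at most seven are null and it is 7/8 × 5.7% = 5.0%.

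**The case against.** - **The seven may already leave out the total score.** Then nothing is loosened. This is possible, but no sentence says so. Counting CGI-S and CGI-I as one endpoint, as protocol 5.1.8 and 12.9.3 do, also gives seven and keeps the duplicate in. The text cannot settle it.
- **The score model is only said to resemble the primary model.** Keeping baseline is an inference. That stands as a condition. If baseline were dropped the p-values would differ, although the analysis would still compare the same outcome at the same visit.
- **Benjamini–Hochberg controls the false discovery rate, not the chance of any false claim.** Correct: with a real HDRS-17 effect, divisor 8 and seven independent nulls, that rate is 7/8 × 5% = 4.4%. But it stays low only because the repeated primary rejection is counted as a tertiary success. Over the other seven alone, every rejection is false in this scenario, so the rate equals the 8.5%.
- **Seven true nulls is an unlikely state once the primary and secondaries have succeeded.** Fair, particularly for the HDRS-based entries. The percentages show how the procedure behaves at that extreme and do not forecast this trial.
- **A reader might infer that the duplicate is certain to be rejected, always loosens the thresholds, and lifts every other endpoint one rank.** The documents do not support that. The gate ensures only p ≤ 0.05. With divisor 8, the duplicate is rejected on its own only at p ≤ 0.00625, and endpoints with smaller p-values keep their rank. For example, with a primary p of 0.04 and a smallest other p of 0.007 (the rest large), 0.007 is rejected in the clean family of seven but not in the family of eight.

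**Conclusion.** The count is contradictory as written, and testing all eight listed endpoints either uses the wrong divisor or lets a repeat of the primary alter the other tertiary thresholds. With divisor 8 the effect has two directions. It loosens when the primary p is at most 0.0125, which is the more common case under the planned effect, and tightens slightly above that. With divisor 7 on eight tests it loosens for a small primary p and does not tighten.

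This rests on four assumptions: baseline HDRS-17 is kept in the score model; the step-up runs at 5%, which SAP 9.2 does not restate for this family; the other seven are null, with independence or correlation 0.5; and the 77% uses the planned effect and conditions on the primary alone, not on the secondaries. Only tertiary claims are affected.

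**What to change.** In SAP 9.2, name the seven endpoints in the tertiary step-up: CGI-S, CGI-I, QIDS-SR-16, HDRS-21, HDRS-17 reduction of at least 7 points, HDRS-17 category shift and Q-LES-Q. State divisor 7. In SAP 8.3 and 11.5.5, mark HDRS-17 total score as descriptive and outside the testing family. No information is lost, since with baseline in the model its p-value is the primary p-value.

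SAP 6 records that the treatment code had not been revealed when the SAP was finalized, so this is a wording change to settle before the final unblinding. The cost is that tertiary thresholds are stricter than with the duplicate included when the primary p is small. When the primary p is nearer 0.05, the first threshold is slightly easier than with divisor 8 (0.00714 instead of 0.00625).
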